#### 7.1.1. Overview of Planned Adverse Events Analyses

The safety analyses will be based on the Safety population unless otherwise specified. [Table 3](#) provides an overview of the planned analyses, with full details of data displays being presented in [Appendix 12](#): List of Data Displays.

**Table 3 Overview of Planned Safety Analyses**

Endpoint / Parameter/ Display Type	Absolute		
	Summary		Individual
	T	F	L
Adverse Events (AEs)			
All AEs by SOC and PT	Y		Y
AEs by GI SOC and PT	Y		
Most Frequent Adverse Events by Overall Frequency	Y		
Drug-Related AEs by SOC and PT	Y		
Subject Numbers for Individual AEs			Y
Relationship Between AE SOCs, PT and Verbatim Text			Y
Serious and Other Significant Events			
All SAEs	Y		Y
Reasons for Considering as a Serious AE			Y
AEs Leading to Withdrawal from Study / Permanent Discontinuation of Study Treatment by SOC and PT	Y		Y
Pregnancy			Y

**NOTES:**

- T = Table, F = Figures, L = Listings, Y = Yes display generated, SOC = System Organ Class, PT = Preferred Term.
- Summary = Represents TF related to any summaries (i.e. descriptive statistics) of the observed raw data.
- Individual = Represents FL related to any displays of individual subject observed raw data.

#### 7.1.1.1. Adverse Events

Adverse events will be assessed for Part 1 and Part 2 separately. Adverse events will be summarized by the cohort of active treatments and pooling of placebo subjects within each part.

An AE is any untoward medical occurrence in a patient or clinical investigation subject, temporally associated with the use of a medicinal product, whether or not considered related to the medicinal product.

No distinction will be made between pre-treatment AEs and treatment emergent AEs in this study, as AE collection is scheduled to start after first dose of study medication.

AE verbatim text will be coded and classified by system organ class (SOC) (body system) and preferred term (PT) using MedDRA (current version 19.0).

AEs will be summarized by number of subjects and percentage of total subjects, by SOC and PT. Summaries and listings will be provided for all AEs, AEs by severity, drug-related AEs, serious AEs, and AEs leading to drug withdrawal.

The details can be found at [Appendix 12](#): List of Data Displays as well as at the file of the mock shell.

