Secondary Analyses	
Pharmacokinetic:
 
 
• Summary Statistics for AUC0-t, AUC0-∞, AUC0-24, Cmax, Tmax, t1/2, Ae, and CLr as data permit;
 
 
Dose Proportionality:
 
 
• Assessment of dose proportionality by AUC0-t, AUC0-∞, and Cmax;
 
 
Pharmacodynamic (TG):
 
 
• Summary statistics for absolute for TG values by treatment and day and Time Point
 
• Summary statistics for Corrected TG by treatment day and time point
 
• Summary statistics for AUC [AUC(1-12), AUC(2-5), Corrected AUC(1-12), Corrected AUC(2-5)] of TG by treatment and day
 
• Summary statistics for percent (%) change from baseline in AUC AUC [AUC(1-12), AUC(2-5), Corrected AUC(1-12), Corrected AUC(2-5)] by treatment and day.
 
 
Pharmacodynamic (BSFS):
 
 
• Summary of number of subjects and number of BSFS by type, day, and treatment
 
• Summary of total number of BSFS by day and treatment
 
 
Pharmacokinetic / Pharmacodynamic
 
 
• PK / PD analyses including correlation and Emax model will not be performed but are recorded in Appendix 9 due to the lack of a repeat dose regimen that was both active for TG suppression and tolerated from a GI perspective.
 

Part 2	
Primary Objective	To characterize the safety, and tolerability of 14 daily repeat doses of GSK3008356 in healthy subjects.
Primary Endpoint	Safety parameters including physical examination findings, vital signs, 12-lead ECGs, continuous lead II cardiac monitoring, clinical laboratory tests and clinical monitoring/observation for adverse events.
Study Design	Repeat Dose Tolerability and PK: this part was a randomized, placebo-controlled, double blind (sponsor unblind), 14-day, repeat-dose, dose-rising study in healthy subjects. There are 3 cohorts with 8 subjects each (6 are on the active drug and 2 are on a matching placebo) while they received a standard 30% fat meal on day - 1, day 1, and day 14, respectively.
Analysis Populations	Screened: Comprised of all subjects who screened which included subjects with screen failure.

Overview	Key Elements of the RAP

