Specifically, **Part 1** doses with PD activity would be progressed into **Part 2**. GI tolerability was not expected to be an issue in **Part 1** and not expected to impact progression into **Part 2**. **Part 2** doses with PD activity and which had tolerability from a GI AE perspective were to be progressed into **Part 3**.

**Part 1** data indicated that single doses of 125 mg or greater were tolerated and had postprandial TG suppression. Divided doses of 45 mg GSK3008356 or greater were tolerated and had postprandial TG suppression. The dose of 45 mg (5 mg hourly for 9 hours) had complete suppression. Divided doses below 45 mg GSK3008356 were not evaluated and exploration of lower divided doses was planned for **Part 2**.

Based on **Part 1** data, the short observed GSK3008356 half-life and future NOAEL identified from a 13 week repeat dose dog toxicology study, **Part 2** initially evaluated placebo or 20 mg GSK3008356 as 10 mg at time 0h and 16h.

Blinded data indicate that 20 mg GSK3008356 divided dosing was not tolerated with 6 of 8 subjects withdrawn early due to GI issues. Dosing was stopped for all subjects before Day 7 of a planned 14 days: 6 due to the GI issues and 2 as the remaining subjects in the cohort were discontinued following discussions between GSK and the Principle Investigator. No PD (postprandial TG suppression) was observed on Day 1; Day 14 could not be evaluated.

Subsequently, placebo or 2 mg GSK3008356 as 1 mg at time 0h and 16h and placebo or 6 mg GSK3008356 as 3 mg at time 0h and 16h were evaluated in Cohorts 2 and 3. All subjects except for 1 in the placebo or 6mg cohort completed the 14 days of dosing, indicating that the doses were tolerated. However, no postprandial TG suppression was observed in either the 2mg or 6mg GSK3008356 divided dosing cohorts.

Based on these data, **Part 2** did not identify a tolerated dose with PD activity and **Part 3** was not initiated.

[figure not shown]
For the purposes of the 204856 RAP, all sections and references pertaining to **Part 3** will be redacted. For any information pertaining to **Part 3** design, objectives and endpoints, please refer to the relevant sections in the protocol. Analysis for **Part 3** is therefore not included in the RAP.

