## 2.4. Study Design

	
75mg, 200mg, 125mg, 200mg divided into 0 hour and 4 hour, 200mg divided into 0 hour and 16 hour, 90mg divided hourly by 9, and 45mg divided hourly by 9, respectively.
 
 
Part 2, 8 subjects receive GSK3008356 (or matching placebo), at a treatment allocation ratio of 6:2, with repeat doses in each of 3 cohorts. The actual doses received are 10mg BID in cohort 1, 1mg BID in cohort 2, and 3mg BID in Cohort 3.
 

--	--

Note: All actual doses start from the morning regardless of the treatment group description.

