### **6.1.4. Drug Exposure**

Exposure will be assessed for Part 1 and Part 2 separately.

For Part 1, the dose received by each subject will be summarized descriptively by cohort of the active treatment.

In Part 2, for each subject, the number of doses, total dose, and the duration (in days) of dosing with the study drug (GSK3008356) will be calculated. These will be listed by subject and summarized descriptively by the cohort active treatment.

The details can be found at [Appendix 12](#): List of Data Displays as well as at the file of the mock shell.

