#### **7.1.1.2. Adverse Event Incidence Rates for All Subjects**

The primary presentation of AE data is prepared without regard to causality or relationship to study medication. Subjects will be counted only once at each level of summarization, by SOC and by PT.

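### In Part 2, crude AE percentages set 10 mg BID (at most 6 dosing days) beside pooled placebo averaging about 11 dosing days, which modestly understates the excess at the highest dose for later-onset events

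*SAP*

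**What the plan says.** SAP section 7.1.1.1 sets the comparison: "Adverse events will be summarized by the cohort of active treatments and pooling of placebo subjects within each part". The measure is a crude proportion: "AEs will be summarized by number of subjects and percentage of total subjects, by SOC and PT". Section 7.1.1.2 adds the counting rule: "Subjects will be counted only once at each level of summarization, by SOC and by PT". Neither SAP Table 3 nor the list of safety tables in Appendix 12 contains a common onset window, an exposure-adjusted rate, or a display of placebo by cohort for AEs.

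The SAP was written after the Part 2 outcome was known. Section 2.4 states: "The actual doses received are 10mg BID in cohort 1, 1mg BID in cohort 2, and 3mg BID in Cohort 3". Section 2.2 says of Cohort 1: "Dosing was stopped for all subjects before Day 7 of a planned 14 days". Of Cohorts 2 and 3 it says: "All subjects except for 1 in the placebo or 6mg cohort completed the 14 days of dosing".

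On exposure, section 6.1.4 derives the number of doses, total dose and duration for each Part 2 subject, then says: "These will be listed by subject and summarized descriptively by the cohort active treatment". Placebo is not named there, although the general Part 2 column layout in Appendix 12 (section 11.12.4) has a placebo column.

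**The concern.** Safety and tolerability are the primary objective of Part 2, and these side-by-side percentages are its main presentation. A percentage of subjects with an event at any time depends on how long the subjects were treated and watched. The SAP already knew that one active cohort had less than half the planned dosing, yet its comparator is mostly placebo subjects from the two cohorts that ran the full 14 days.

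Background events therefore have more time to accrue on placebo and at the lower doses than at the highest dose, and late effects of 10 mg BID had no dosing time in which to appear. Both push the visible excess at the highest dose downwards. The reading most affected is the dose and placebo comparison for events that do not cluster in the first days.

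**Working it through.** **Inputs**
- Part 2: 3 cohorts of 8, allocated 6 active to 2 placebo (SAP synopsis; SAP 2.4). That makes 3 x 8 = 24 subjects, matching the approximate 24 in protocol section 3.2, with 3 x 2 = 6 on placebo.
- Cohort 1, active and placebo: at most 6 dosing days (SAP 2.2).
- Cohorts 2 and 3: 14 days for all but one Cohort 3 subject, whose arm is not stated (SAP 2.2).
- AEs are collected from the start of treatment to the follow-up contact (protocol 6.3.1.1). Planned follow-up is Day 20-22 (SAP 11.2.1.5), which is 6 to 8 days after Day 14. Its timing for subjects stopped early is not stated.

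The documents give no exposure ratio to reproduce.

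**Dosing days**
- Pooled placebo: (2 x 6 + 4 x 14)/6 = 68/6 = 11.3 days. Ratio to 10 mg BID: 11.3/6 = 1.89.
- If the Cohort 3 non-completer was on placebo and stopped on Day 1: (12 + 42 + 1)/6 = 9.17, ratio 1.53. If on Day 13: (12 + 42 + 13)/6 = 11.17, ratio 1.86.
- Six days is a ceiling. If Cohort 1 averaged 4 days in both arms: (2 x 4 + 4 x 14)/6 = 10.67, ratio 10.67/4 = 2.67.
- Lower-dose completers against 10 mg BID: 14/6 = 2.33 or more.

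**Observation days**
- Follow-up 6 days after the last dose: (2 x 12 + 4 x 20)/6 = 17.33 against 12, ratio 1.44.
- Follow-up 8 days after the last dose: (2 x 14 + 4 x 22)/6 = 19.33 against 14, ratio 1.38.
- Follow-up kept at Day 20-22 for everyone: ratio 1.0.

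**Size of the bias**

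Assume a constant daily background hazard, a 14-day risk p14 (not in the documents, so shown as a range), and both Cohort 3 placebo subjects completing. The risk over d days is p(d) = 1 - (1 - p14)^(d/14).

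Counting on-treatment onset only, the like-for-like value is p(6) and the planned comparator is [2 p(6) + 4 p14]/6. Counting to a follow-up 8 days after the last dose, these become p(14) and [2 p(14) + 4 p(22)]/6.

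| Assumed p14 | On-treatment: like-for-like | On-treatment: pooled | Bias (points) | To follow-up: like-for-like | To follow-up: pooled | Bias (points) |
|---|---|---|---|---|---|---|
| 10% | 4.4% | 8.1% | 3.7 | 10.0% | 13.5% | 3.5 |
| 20% | 9.1% | 16.4% | 7.3 | 20.0% | 26.4% | 6.4 |
| 30% | 14.2% | 24.7% | 10.5 | 30.0% | 38.6% | 8.6 |

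If follow-up stayed at Day 20-22 for everyone, the bias for pure background events is zero. One placebo subject of six is 16.7 points.

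**GI withdrawals**

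Six of the eight Cohort 1 subjects were withdrawn for GI issues (SAP 2.2, blinded). At most two of them were on placebo, so at least 6 - 2 = 4 of the 6 active subjects were.

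**The case against.** The strongest reply is that dosing days are the wrong clock. AEs count to the follow-up contact and no table restricts them to on-treatment onset, so the relevant ratio is 1.0 to 1.44. That stands, and the dosing-day ratio must be labelled as such. It does not end the matter. The timing of follow-up for early-stopped subjects is not given, and with an observed half-life of 1.5 to 3 hours (SAP 2.1) the days after stopping are effectively off drug. Even with equal observation, 10 mg BID would be watched mostly off treatment and its comparators mostly on it.

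Second, the analysis is descriptive and the bias is below one placebo subject of six. That also stands and limits the weight of the point. It does not justify leaving a foreseeable imbalance in the main comparison when correcting for it is cheap.

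Third, much is visible already. Stool data are summarised by type, day and treatment (SAP 8.2.1.3; Tables 5.9-5.12). Table 1.3 shows discontinuations, AEs leading to withdrawal have their own tables, and exposure and AEs are listed by subject. This is right, so the imbalance is not concealed. The AE percentages themselves, however, are not aligned in time.

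The SAP accepts the principle elsewhere: it keeps Cohort 8 placebo out of the Part 1 triglyceride pool because a second meal made those subjects non-comparable (section 8.2.1.1).

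**Conclusion.** The point holds in a limited form. In expectation, the planned tables understate the excess at 10 mg BID, against placebo and against the lower doses, for AEs that can start after the first days. The bias is about 4 to 11 points for on-treatment onset, given a constant hazard and an assumed 14-day background risk of 10% to 30%. Counting AEs to follow-up, it lies between zero and about 9 points at the same risks, taking follow-up 8 days after the last dose as the unequal case.

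A reader might infer three stronger things that the documents do not support:
- **That placebo was observed for nearly twice as long.** The ratio of 1.9 is for dosing days only. By the same token, the claim that a drug raising the hazard about 1.86-fold would look like placebo holds only for on-treatment onset.
- **That every AE at the highest dose is understated.** Events in the first days are hardly affected.
- **That the GI signal could be hidden or the GI dose-response reversed.** At least 4 of 6 active Cohort 1 subjects were withdrawn for GI issues, while all but one subject in the lower-dose cohorts completed 14 days.

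**What to change.** Keep the planned AE tables. For the Part 2 versions of the all-AE, GI, most-frequent and drug-related tables (3.2, 3.4, 3.6 and 3.8, taking the second number of each pair as Part 2), add a supplementary version limited to onset on Days 1-6 in all four groups. Read it beside the overall tables for the dose and placebo comparison. Base the filter on onset time since first dose, already derived in SAP 11.4.2.1, not on study day, which SAP 11.6.1 counts from randomisation. In SAP 6.1.4, state that the Part 2 exposure summary includes the pooled placebo column in dosing days.

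The cost is a few extra tables from existing programs, with no new data. The supplementary tables leave out later-onset events. They also do not fully equalise dosing, because some Cohort 1 subjects may have stopped before Day 6. For both reasons they supplement the overall tables and do not replace them.

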#### **7.1.1.2. Adverse Event Incidence Rates for All Subjects**

The primary presentation of AE data is prepared without regard to causality or relationship to study medication. Subjects will be counted only once at each level of summarization, by SOC and by PT.

#### **7.1.1.3. Severity of Adverse Events**

The investigator makes assessment of intensity for each AE reported during the study and assigns it to one of the following categories:

- **Mild:** An event that is easily tolerated by the subject, causing minimal discomfort and not interfering with everyday activities.
- **Moderate:** An event that is sufficiently discomforting to interfere with normal everyday activities.
- **Severe:** An event that prevents normal everyday activities.

AEs will be summarized by severity. If a subject has multiple occurrences of the same SOC or PT, then it will be counted as the maximum severity among them.

#### **7.1.1.4. Relationship to Study Treatment**

For each AE, the investigator will assess the relationship between study treatment and the AE occurrence, using clinical judgment. The investigator will provide a YES / NO answer to the question “Is there a reasonable possibility that the AE may have been caused by the study treatment? Use best judgment at initial entry. May be amended when additional information becomes available.”

The subset of AEs which are classified as “related” (answer = YES) will be summarized in the same way as all AEs (Section 7.1.1).

The details can be found at [Appendix 12](#): List of Data Displays as well as at the file of the mock shell.

**7.1.1.5. Serious Adverse Events (SAE), Adverse Events Leading to Drug Discontinuation, and Death**

The subset of AEs which are serious (SAEs) and/or lead to discontinuation of study drug, withdrawal from the study, or death will be summarized in the same way as all AEs (Section 7.1.1.2). These AEs will be listed, indicating “serious” and/or the outcome.

The results of pregnancy testing will be listed. The details can be found at [Appendix 12](#)-List of Data Display as well as the file of the mock shell.

**7.1.2. Overview of Planned Clinical Laboratory Analysis**

The safety analyses will be based on the Safety population, unless otherwise specified.

[Table 4](#) provides an overview of the planned analyses, with further details of data displays being presented in [Appendix 12](#): List of Data Displays.

**Table 4 Overview of Planned Clinical Laboratory Analyses**

Endpoint / Parameter/ Display Type	Absolute			Change from BL		
	Summary		Individual	Summary		Individual
	T	F	L	T	F	L
Chemistry						
Chemistry Changes from Baseline				Y		
Hematology						
Hematology Changes from Baseline				Y		
Urinalysis						
Urine Concentration Changes from Baseline				Y		
Urinalysis Dipstick Results	Y					
Hepatobiliary (Liver)						
Liver Monitoring/Stopping Event Reporting	Y		Y			
Matrix Display of Maximum LFT (ALT, AST, ALP, and Total Bilirubin) Values		Y				
Individual LFT (ALT, AST, ALP, and Total Bilirubin) Values versus Study Time by Treatment Group and Test		Y				
All Laboratory						
All Laboratory Data for Subjects with any Value of Potential Clinical Concern/PCI			Y			

Endpoint / Parameter/ Display Type	Absolute			Change from BL		
	Summary		Individual	Summary		Individual
	T	F	L	T	F	L
Laboratory Values of PCI			Y			

**NOTES:**

- T = Table, F = Figures, L = Listings, Y = Yes display generated, PCI = Potential Clinical Importance
- Summary = Represents TFL related to any summaries (i.e. descriptive statistics) of the observed raw data.
- Individual = Represents FL related to any displays of individual subject observed raw data.

**7.1.2.1. Clinical Laboratory**

Clinical laboratory results will be assessed for Part 1 and Part 2 separately. Laboratory evaluations will be summarized by the cohort of active treatments and pooling of placebo subjects within each part.

Clinical laboratory evaluations are divided into:

- **Haematology:** Platelet Count, RBC Count, WBC Count (absolute), Reticulocyte Count, Hemoglobin, Hematocrit, MCV, MCH, MCHC, Neutrophils, Lymphocytes, Monocytes, Eosinophils, Basophils;
- **Clinical Chemistry:** BUN, Creatinine, Glucose, Sodium, Bile Acids, Potassium, Chloride, bicarbonate, Calcium, AST (SGOT), ALT (SGPT), GGT, Alkaline phosphatase, Total and direct bilirubin, Uric Acid, Albumin, Total Protein;
- **Urinalysis:** Specific gravity, pH, glucose, protein, blood, ketones, Microscopic examination;
- **Liver Function Tests (LFTs):** total bilirubin, ALT.

Tables with descriptive statistics of change from baseline will be produced for all numerical tests for subjects with non-missing assessments. For categorical tests the number and percent of subjects for each category will be produced. Prior to analysis, all applicable numeric assessments will be converted to standard units.

Listing of all laboratory data for subjects with any value of PCI will be produced.

Listings of laboratory data with any value of PCI will be produced, too.

A listing will be created for subjects with any post baseline Liver Function Test (LFTs) with other Laboratory parameters, i.e. one of ALT and total bilirubin, classified as PCI..

Special figures, “matrix displays”, will be produced showing pairwise plots of the LFT values. To create these plots, the maximum value (over time) for each subject for each LFT will be calculated. Then for each pair of tests (e.g., total bilirubin vs ALT), each

subject will be plotted on the chart according to the maximum value of each. The subject markers (color and symbol) will be coded according to part /treatment.

